## 9.2 Methods and Timing for Assessing, Recording, and Analyzing Safety Parameters

### 9.2.1 Adverse Events

An adverse event (AE) includes any noxious, pathological or unintended change in anatomical, physiological or metabolic functions as indicated by physical signs, symptoms and/or laboratory-detected changes occurring in any phase of the clinical study, whether associated with the study product (i.e., vaccine, placebo or CHHI), and whether or not considered study product related. This includes an exacerbation of pre-existing conditions and intercurrent illnesses.

All AEs will be graded for severity and relationship to study vaccine or to CHHI. A licensed clinician (i.e. physician, nurse practitioner, physician assistant) listed on the Form FDA 1572 will be readily available for the duration of the trial to assess AEs. Should a subject call on a study clinician to report an AE, it will be fully documented in their study chart, and discussed with the Principal Investigator.

All AEs will be assessed by the investigator using the following protocol-defined grading system, as or described in **Tables 1-5**:

- Grade 1: **Mild** - No effect on activities of daily living; no medical intervention/therapy required
- Grade 2: **Moderate** - Partial limitation in activities of daily living (can complete  $\geq 50\%$  of baseline); no or minimal medical intervention/therapy required
- Grade 3: **Severe** - Activities of daily living limited to  $< 50\%$  of baseline; medical evaluation/therapy required

All AEs will have their possible relationship to study vaccine or CHHI assessed using the following terms:

- Definite: Clear-cut temporal association, and no other possible cause.
- Probable: Clear-cut temporal association and a potential alternative etiology is not apparent.
- Possible: Less clear temporal association; other etiologies also possible.
- Unlikely: Temporal association between the AE and the study product or the nature of the event is such that the study product is not likely to have had any reasonable association with the observed illness/event (cause and effect relationship improbable but not impossible).
- Not Related: The AE is completely independent of study product administration; and/or evidence exists that the event is definitely related to another etiology.

The degree of certainty with which an AE can be attributed to administration of study product will be determined by how well the event can be understood in terms of one or more of the following:

1. The event being temporally related with vaccination (or CHHI) or reproduced on re-vaccination.

2. A reaction of similar nature having previously been observed with this study product.
3. The event having often been reported in the literature for similar types of vaccines or for CHHI.

### 9.2.2 Vaccine Reactogenicity

All subjects will be observed for at least 60 minutes after each study vaccination to detect and treat any immediate AEs. Subjects will also complete study memory aids after each vaccination beginning with the day of vaccination and through 14 days after vaccination. Injection site reactions including bruising, redness, induration (hardness)/swelling, pain, and tenderness will be recorded on the study aids. Systemic reactions including fever, myalgia (body aches/muscular pains exclusive of the injection site), arthralgia (joint pains exclusive of the injection site), headache, nausea, and vomiting will also be recorded.

Subjects will also be asked to record any medications taken and any emergency room or healthcare provider visits (other than routine check-ups). The subject memory aid will be reviewed with the subject at subsequent clinic visits.

Vaccine reactogenicity events are AEs that are known to occur with types of vaccine similar in composition to those being tested in this study. The following Toxicity Grading Scales will be used to grade solicited local (injection site) and systemic (subjective and quantitative) reactions:

**Table 1: Assessment of Solicited or Expected Adverse Event Severity – Vaccination Phase**

Adverse Event	Grade	Severity
Pain at injection site	1	Aware of pain but it does not interfere with daily activity and no pain medication is taken
	2	Aware of pain; there is interference with daily activity or it requires use of pain medication
	3	Aware of pain and it prevents daily activity
Tenderness at injection site	1	Area immediately surrounding injection site hurts only when touched or with arm motion, and it does not interfere with daily activity
	2	Area immediately surrounding injection site hurts when touched or with arm motion, and it interferes with daily activity
	3	Area immediately surrounding injection site hurts when touched or with arm motion, and it prevents daily activity
Erythema at injection site	1	25 mm – 50 mm
	2	51 mm – 100 mm
	3	> 100 mm
Induration/swelling at injection site	1	25 mm – 50 mm and does not interfere with daily activity
	2	51 mm – 100 mm or interferes with daily activity
	3	>100 mm or prevents daily activity
Fever* (oral†)	1	38.0°C – 38.4°C
	2	38.5°C – 38.9°C
	3	>39.0°C
Headache	1	Easily tolerated, does not interfere with daily activity
	2	Repeated use of non-narcotic pain reliever for >24 hours or interferes with daily activity
	3	Any use of narcotic pain reliever or prevents daily activity

Nausea	1	Easily tolerated, does not interfere with daily activity
	2	Interferes with daily activity
	3	Prevents daily activity
Vomiting	1	1-2 episodes in 24 hours and does not interfere with activity
	2	> 2 episodes in 24 hours or interferes with daily activity
	3	Prevents daily activity or requires outpatient IV hydration
Myalgia**	1	Easily tolerated, does not interfere with daily activity
	2	Interferes with daily activity
	3	Prevents daily activity
Arthralgia**	1	Easily tolerated, does not interfere with activity
	2	Interferes with daily activity
	3	Prevents daily activity

\* Oral temperature assessed on Day 0 (Visit 1) prior to the first study vaccination will be considered as baseline. Temperatures obtained during the clinic visits will be recorded.

† Subjects must not eat or drink anything hot or cold, or smoke within 10 minutes prior to taking oral temperature.

\*\* Not at injection site.

**Table 2: Assessment of Unsolicited Systemic Adverse Event Severity – Vaccination Phase**

Systemic AE	Mild (Grade 1)	Moderate (Grade 2)	Severe (Grade 3)
Anorexia	Loss of appetite without decreased oral intake lasting greater than 48 hours	Loss of appetite associated with decreased oral intake without significant weight loss	Loss of appetite associated with significant weight loss
Diarrhea	3 loose stools/24 hours	4-5 loose stools/24 hours	>6 loose stools or requires outpatient IV hydration
Constipation	Not Applicable	Persistent constipation requiring regular use of dietary modifications, laxatives, or enemas	Obstipation with manual evacuation indicated
Fatigue	No interference w/activity	Some interference w/activity	Significant, prevents daily activity
Arthritis	Mild pain with inflammation, erythema or joint swelling – but not interfering with function	Moderate pain with inflammation, erythema or joint swelling – interfering with function, but not with activities of daily living	Severe pain with inflammation, erythema or joint swelling –and interfering with activities of daily living
Vasovagal episode (associated with a procedure of any kind)	Present without loss of consciousness	Present with transient loss of consciousness	Not Applicable
Vertigo	Causes no or minimal interference	Causes greater than minimal interference	Inability to perform daily activities

	with usual daily activities	with usual daily activities	
Cough	Transient- no treatment	Persistent cough; treatment responsive	Paroxysmal cough; uncontrolled with treatment
Bronchospasm, Acute	Transient; no treatment; 70% - 80% FEV 1 of peak flow	Requires treatment; normalizes with bronchodilator; FEV 1 50% - 70% (of peak flow)	No normalization with bronchodilator; FEV 1 25% - 50% of peak flow; or retractions present
Dyspnea	Dyspnea on exertion	Dyspnea with normal activity	Dyspnea at rest
Hypersensitivity	Transient flushing or rash	Rash; flushing; urticaria; dyspnea	Symptomatic bronchospasm, with or without urticaria; parenteral medications(s) indicated; allergy-related edema/angioedema; hypotension
Urticaria	Requiring no medications	Requiring PO or topical treatment, or IV medication or steroids for <24 hours	Requiring IV medication or steroids for >24 hours

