### **9.2.5 Serious Adverse Events**

An SAE is an AE, whether considered related to a study product or not, meeting one of the following conditions:

1. Death during the period of protocol-defined surveillance
2. Life threatening: defined as an event that places a subject at immediate risk of death at the time of the event and does not refer to an event that hypothetically might have caused death were it more severe
3. Hospitalization during the period of protocol-defined surveillance: defined as at least an overnight stay in the hospital or emergency ward for treatment that would have been inappropriate if administered in the outpatient setting
4. Results in a congenital anomaly or birth defect
5. Results in a persistent or significant disability or incapacity: defined as a substantial disruption of the study subject's ability to carry out normal life functions
6. Any other important medical event that may not result in death, be life threatening, or require hospitalization, may be considered a serious AE when, based upon appropriate medical judgment, the event may jeopardize the subject and may require medical or surgical intervention to prevent one of the outcomes listed above.

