## **9.5 Halting Rules**

If the study vaccine or CHHI is considered significantly reactogenic or results in significant AEs (see below and **Section 9.2**), additional vaccinations or CHHIs will be suspended until reviewed by the SMC, Independent Safety Monitor, DMID Medical Monitor, and IND sponsor (BCM). Any recommendation of the Independent Safety Monitor, DMID Medical Monitor, and SMC to resume or suspend further injections or CHHIs (either for an individual subject or the full study) will be communicated in writing to the sponsor and Principal Investigator. All communications from the SMC will subsequently be forwarded by the investigators to the IRB.

The following criteria will be used to define significant reactogenicity:

- One or more participants experience a protocol defined SAE that is determined to be possibly, probably, or definitely related to a study vaccine or CHHI, **OR**,
- One or more participants experience a protocol defined AESI that is determined to be possibly, probably, or definitely related to a study vaccine or CHHI, **OR**,
- One or more participants experience a protocol defined Grade 3 hypersensitivity reaction that is possibly, probably or definitely related to a study vaccine or CHHI, **OR**,
- Two or more participants experience a protocol defined Grade 2 hypersensitivity reaction that is probably or definitely related to a study vaccine or CHHI, **OR**,
- Three or more participants experience the same objective physical finding or laboratory abnormality of Grade 3 or higher (with the exception of isolated Grade 3 erythema or swelling at the site of vaccination or Grade 3 erythema and/or rash at the site of application of the larvae), that is determined to be probably or definitely related to a study vaccine or CHHI, **OR**,
- Three or more participants experience the same Grade 2 or higher safety laboratory abnormality (excluding eosinophilia [or increased white blood cell count secondary to eosinophilia] after CHHI) or Grade 3 clinical AE that is possibly, probably or definitely related to a study vaccine or CHHI.

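### Table 2 grades the same urticaria differently in two rows, and no sentence says that urticaria alone takes the Hypersensitivity grade for the halting rules

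*Protocol*

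**What the plan says.** Protocol 9.2.2, Table 2, grades unsolicited systemic events. Under 9.2.3 it also grades unsolicited events after the larval challenge. Two of its rows cover urticaria.

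- **Hypersensitivity row.** Grade 1 covers only passing flushing or rash. Grade 2 reads "Rash; flushing; urticaria; dyspnea". Grade 3 lists several features, among them "parenteral medications(s) indicated", with no minimum duration.
- **Urticaria row.** Grade 1 is "Requiring no medications". Grade 2 is "Requiring PO or topical treatment, or IV medication or steroids for <24 hours". Grade 3 is "Requiring IV medication or steroids for >24 hours".

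Section 9.2.1 makes the general scale and Tables 1 to 5 together the grading system of the protocol.

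Section 9.5 lists the halting criteria as bullets, numbered here in order. Criterion 3 is "One or more participants experience a protocol defined Grade 3 hypersensitivity reaction that is possibly, probably or definitely related" to a study vaccine or the challenge. Criterion 4 is "Two or more participants experience a protocol defined Grade 2 hypersensitivity reaction that is probably or definitely related to a study vaccine or CHHI".

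**The concern.** Criteria 3 and 4 are count rules. Once the count is reached, vaccinations and challenges stop until review, and no one has to exercise judgment first. Such a rule works only if each event has one grade. Here a clinician who records generalized hives can reasonably turn to the row called Urticaria, grade the event there, and obtain a lower grade than the Hypersensitivity row gives. The event may then never be counted.

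Urticaria is a foreseeable kind of event in this programme. Section 2.1.3 reports that generalized urticaria stopped vaccinations in a trial of an earlier hookworm antigen, and 2.3.1.2 names urticaria among the possible immediate hypersensitivity reactions.

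**Working it through.** The plan states no figure on this point, so there is none to reproduce. The check sets the two rows side by side and passes each grade through the two criteria.

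**Step 1: grades from Table 2.** The items within each Hypersensitivity cell are read as alternatives.

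| Treatment of the urticaria | Hypersensitivity row | Urticaria row | Same? |
|---|---|---|---|
| No medication | 2 | 1 | No |
| Oral or topical | 2 | 2 | Yes |
| Intravenous, under 24 h | 3 | 2 | No |
| Intravenous, over 24 h | 3 | 3 | Yes |

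The rows disagree at two levels. At both, the Hypersensitivity row gives the higher grade.

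**Step 2: what each grade triggers under 9.5.**

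- Grade 3: one participant, possibly, probably or definitely related (criterion 3).
- Grade 2: two participants, probably or definitely related (criterion 4). A case that is only possibly related does not count.
- Grade 1: neither criterion.

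**Step 3: participants needed to meet criterion 3 or 4**, counting urticaria as a hypersensitivity reaction on either row.

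| Case | Relatedness | Hypersensitivity row | Urticaria row |
|---|---|---|---|
| No medication | Probable or definite | 2 | Never met |
| Intravenous, under 24 h | Probable or definite | 1 | 2 |
| Intravenous, under 24 h | Possible only | 1 | Never met |

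Untreated cases that are only possibly related meet neither criterion on either row.

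**Step 4: do criteria 5 and 6 close the gap?** No. Each needs three participants, and for a clinical event each needs Grade 3. The Urticaria row gives Grade 1 or 2 at the two levels in conflict.

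**Step 5: is there a rule of precedence?** None appears in 9.2, in 9.5 or in the SAP. SAP 5.7.5.1 counts only the most severe event when tabulating by severity. That applies after a grade has been assigned and does not say which row assigns it.

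**The case against.** The strongest answer is that 9.5 already points to one row. Criteria 3 and 4 speak of hypersensitivity reactions, Table 2 has one row with that name, and that row lists urticaria. Sections 2.1.3 and 2.3.1.2 both class vaccine-induced urticaria as hypersensitivity. This stands as the natural reading. A reader might infer from the overlap that the two criteria have no defined grade at all, and the documents do not support that. What remains is narrower. Because 9.2.1 gives both rows equal standing, nothing tells the person grading isolated urticaria to pass over the row that bears its name.

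The second answer is that other provisions would catch a worrying case.

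- 9.2.5, item 6: "Any other important medical event that may not result in death, be life threatening, or require hospitalization, may be considered a serious AE". A related case judged this way meets criterion 1.
- 9.6 lets the Independent Safety Monitor put the study on hold at any time. Section 4 adds stopping on the clinical judgment of the Safety Monitoring Committee, the Independent Safety Monitor or the Medical Monitor.
- 5.3.3 allows the next dose or the challenge to be withheld from the affected person.

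These limit the consequence considerably. They do not replace the count rules, since the first two rest on discretion and the third protects one participant and does not pause the study.

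Third, the event is expected to be uncommon. Section 2.1.4 reports that none of 179 confirmatory sera exceeded the clinical IgE cut-off and judges immediate hypersensitivity to this antigen unlikely. Section 5.2 excludes people with a history of severe allergic reaction. This also stands, and it is a reason to rate the point low.

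**Conclusion.** The point holds as a minor inconsistency in a safety rule. Table 2 gives two grades to untreated urticaria and to urticaria treated intravenously for under 24 hours, and no sentence says which one criteria 3 and 4 take when urticaria occurs alone. The size is the difference in case counts shown above. The documents give no urticaria rate for this vaccine, so no probability of a missed halt is attached. No efficacy analysis is affected.

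The conclusion assumes that the items in the Hypersensitivity cells are alternatives and that the urticaria is judged related to vaccine or challenge.

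A reader might also infer a third conflict in the opposite direction, with oral steroids for over 24 hours at Grade 3 on the Urticaria row and Grade 2 on the Hypersensitivity row. That requires the word steroids in the Urticaria row to include oral steroids. The same row already places oral treatment at Grade 2 with no time limit, so steroids more naturally goes with intravenous. The text does not settle this, and the third conflict is not counted here.

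**What to change.** Add one sentence to 9.5: *For criteria 3 and 4, systemic urticaria that is related to study vaccine or CHHI counts as a hypersensitivity reaction and takes the higher of the grades given by the Hypersensitivity and Urticaria rows of Table 2.*

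The relatedness thresholds already in each criterion stay as they are. The word systemic keeps local rash at the larval application site, which Table 3 grades, out of the count. Taking the higher grade also works whichever way the steroid wording is read.

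The Urticaria row need not be rewritten. Raising its grades would raise the tabulated severity of all urticaria, including unrelated cases that these criteria do not count.

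The cost is one sentence in an amendment and a slightly greater chance of a precautionary pause for mild urticaria.

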### 9.2.3 CHHI Reactogenicity

All subjects will be observed for at least 60 minutes after application of the *N. americanus* larvae during CHHI to detect and treat any immediate AEs. Subjects will also complete study memory aids after CHHI beginning with the day of larval application and through Day 280 when they will be treated with albendazole to cure their infections. For the first 4 weeks after application of the *N. americanus* Larval Inoculum, the memory aids will be used to record pruritus, pain, tenderness, rash and swelling at the site of larval application, as well as cough and sore throat (to capture symptoms that may possibly be related to larval migration through the lungs). Starting on Day 175 (approximately 5 weeks after CHHI) of the study until the participant receives their first dose of albendazole, the memory aids will be used to record nausea, vomiting, diarrhea, abdominal pain, abdominal bloating and flatulence. Female participants of childbearing potential will additionally capture on the memory aids the form of contraception they are using. The memory aids will include a printed reminder of the potential risks associated with use of albendazole during pregnancy.

Subjects will also be asked to record any medications taken and any emergency room or healthcare provider visits (other than routine check-ups) through Day 297. The subject memory aid will be reviewed with the subject at subsequent clinic visits.

CHHI reactogenicity events are AEs that are known to occur with hookworm infection. The following Toxicity Grading Scales will be used to grade solicited local (larval application site) and systemic (subjective and quantitative) reactions:

**Table 3: Assessment of Solicited or Expected Adverse Event Severity – CHHI Phase**

Adverse Event	Grade	Severity
Pain at site of larval application	1	Aware of pain but it does not interfere with daily activity and no pain medication is taken
	2	Aware of pain; there is interference with daily activity or it requires use of pain medication
	3	Aware of pain and it prevents daily activity
Tenderness at site of larval application	1	Area immediately surrounding application site hurts only when touched or with arm motion, and it does not interfere with daily activity
	2	Area immediately surrounding application site hurts when touched or with arm motion, and it interferes with daily activity
	3	Area immediately surrounding application site hurts when touched or with arm motion, and it prevents daily activity
Rash at site of larval application	1	25 mm – 50 mm and does not interfere with daily activity
	2	51 mm – 100 mm or interferes with daily activity
	3	> 100 mm or prevents daily activity
Induration/swelling at site of larval application	1	25 mm – 50 mm and does not interfere with daily activity
	2	51 mm – 100 mm or interferes with daily activity
	3	> 100 mm or prevents daily activity
Pruritus at site of larval application	1	Easily tolerated, does not interfere with daily activity
	2	Interferes with daily activity
	3	Prevents daily activity
Abdominal pain	1	Easily tolerated, does not interfere with daily activity
	2	Interferes with daily activity
	3	Prevents daily activity
Abdominal bloating	1	Easily tolerated, does not interfere with activity
	2	Interferes with daily activity
	3	Prevents daily activity
Nausea	1	Easily tolerated, does not interfere with daily activity
	2	Interferes with daily activity
	3	Prevents daily activity
Vomiting	1	1-2 episodes in 24 hours and does not interfere with activity
	2	> 2 episodes in 24 hours or interferes with daily activity
	3	Prevents daily activity or requires outpatient IV hydration
Diarrhea	1	2-3 loose stools/24 hours
	2	4-5 stools/24 hours
	3	> 6 loose stools or requires outpatient IV hydration
Flatulence	1	Easily tolerated, does not interfere with daily activity
	2	Interferes with daily activity
	3	Prevents daily activity
Cough	1	Easily tolerated, does not interfere with daily activity
	2	Interferes with daily activity
	3	Prevents daily activity
Sore throat	1	Easily tolerated, does not interfere with daily activity
	2	Interferes with daily activity
	3	Prevents daily activity

The severity of unsolicited adverse events post-CHHI will be graded as per Table 2 above.

#### 9.2.4 Additional Adverse Event Severity Grading

Pulse and blood pressure will be graded as follows (Table 4):

**Table 4: Assessment of Basic Body Function Adverse Event Severity**

Vital Signs*	Mild (Grade 1)	Moderate (Grade 2)	Severe (Grade 3)
Tachycardia – beats per minute (bpm)	101-115	116-130	>130
Bradycardia – beats per minute	50 - 54 or 45-50 bpm if baseline <60 bpm	45 - 49 or 40-44 if baseline <60bpm	< 45 or <40bpm if baseline <60bpm
Hypertension** (systolic, mm Hg)	141-150	151-155	>155
Hypertension** (diastolic, mm Hg)	91-95	96-100	>100
Hypotension** (systolic, mm Hg)	85-89 (and symptomatic)	80-84 (and symptomatic)	<80
Respiratory Rate – breaths per minute	18-20	21-25	>25

\*Subject should be at rest for measurement of vital signs

\*\*With repeat testing at same visit

